#### **4.4 RESIDUAL RISKS ASSOCIATED WITH THE DEVICE**

A risk analysis of the Carry Life® UF system has been performed according to ISO 14971:2019 and is available in Appendix C of the IB. The Carry Life® UF system complies to identified applicable regulatory standards and the risk analysis shows that the usage of the Carry Life® UF does not entail unacceptable risks.

The residual risks associated with the device have been reduced to an acceptable level or as a low level as reasonably possible. Further mitigation will not improve safety. The risk level for contamination is comparable to conventional PD therapies. From a general risk-benefit perspective, the risk posed by the clinical investigation performed by the Carry Life® UF system is acceptable and comparable to standard methods of PD.

#### **4.5 RISKS ASSOCIATED WITH PARTICIPATION IN THE CLINICAL INVESTIGATION AND MITIGATION**

Risks associated with participation in the clinical investigation have been evaluated according to ISO 14971:2019. Risks with the clinical investigation are similar to standard CAPD treatment including hyper- or hypovolemia, hyper- or hypo glycemia, as well as risk associated with blood sampling. Risks of additional blood sampling, PET/CAPD dwell during in-clinic phase, and Carry Life UF® treatments in clinic, will be performed by healthcare professionals at the PD clinic according to routine clinical procedures. Risks associated with Carry Life UF® treatments at home during the home treatment phase will be mitigated by PD patients being trained in aseptic technique and on the Carry Life UF® treatment, furthermore a study nurse shall be present during the preparation and initiation of the first at home treatment. Diabetic patients on insulin frequently monitor blood glucose levels according to their regular diabetes management and are familiar with early symptoms of hypo-/hyper-glycemia and how to manage this.

Refer to Table 6 for a list of adverse effects associated with PD compared to the Carry Life® UF system and their study mitigations.

#### 4.6 POSSIBLE INTERACTIONS WITH CONCOMITANT MEDICAL TREATMENTS

A concomitant therapy is any drug or substance administered between the time the patient has been enrolled and the completion of the follow-up/end of the clinical investigation. Adjustments to medication regimes can be performed at the discretion of the Investigator and should be documented in the electronic case report form (eCRF) (assessments/evaluations) and medical records. Blood concentration of dialysable drugs can be reduced by PD but no change is expected when introducing the Carry Life® UF system as the amount of PD fluid used will not be changed during the study. Glucose has no known drug interaction with the Carry Life® UF system.

#### 4.7 BENEFIT TO RISK RATIONALE

Based on the above assessments of the benefits and risks with the Carry Life® UF system, it can be concluded that the benefits exceed the risks for patients included in the clinical investigation and may significantly benefit future PD patients. The risks associated with the study treatment are the same as the risks associated with standard PD therapies.

## 5 OBJECTIVES OF THE CLINICAL INVESTIGATION

---

### 5.1 OBJECTIVES

#### 5.1.1 Primary objective

The primary objective of the clinical investigation is:

- To demonstrate that a 5-hour Carry Life® UF treatment at home results in an increased UF volume compared to a 5-hour 2.27% glucose CAPD dwell in adult CAPD patients.

#### 5.1.2 Secondary objectives

The secondary objectives of the clinical evaluation are:

- To evaluate the overall safety of the Carry Life® UF system used by the patient at home as measured by rates of adverse events (AEs) and serious adverse events (SAEs) in adult CAPD patients.
- To demonstrate that treatment with the Carry Life® UF system at home results in increased sodium removal compared to a 2.27% glucose CAPD dwell in adult CAPD patients.
- To demonstrate that treatment with the Carry Life® UF system at home results in a more glucose efficient peritoneal fluid removal compared to a 2.27% glucose CAPD dwell in adult CAPD patients.
- To evaluate if the peak glucose concentration during a Carry Life® UF treatment is lower than the glucose concentration of a 2.27% glucose PD solution.

#### 5.1.3 Exploratory objectives

The exploratory objectives of the clinical evaluation are:

- Evaluation of peritoneal urea and creatinine removal.
- Evaluation of overall weekly UF based on the patient diary.

### 5.2 HYPOTHESES TO BE ACCEPTED OR REJECTED BY STATISTICAL DATA FROM THE CLINICAL INVESTIGATION

#### Primary endpoint hypothesis

The UF volume achieved with the Carry Life® UF system is superior compared to the UF volume achieved with CAPD using a 2.27% glucose PD solution during a 5-hour treatment.

Hypothesis:

:  $H_0: \mu_d \leq \delta$   
H1:  $\mu_d > \delta$

Where  $\mu_d$  is the average paired difference in UF volume and  $\delta$  is the superiority margin of 250 ml.

Where  $H_0$  is rejected if the following is true:

$$\frac{(\hat{\epsilon} - \delta)}{\frac{\hat{\sigma}_m}{\sqrt{2n}}} < t_{\alpha, 2n-2}$$

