### 6.3 SUBJECTS

#### 6.3.1 Subject selection

The patients to be recruited in the clinical investigation have been on stable PD therapy for ESKD for at least three months and with a PD prescription of 2-4 CAPD dwells/day, unchanged for a minimum of two weeks, with at least one 1.5-2 L 2.27% glucose day dwell daily.

Should a change of the PD prescription be necessary for a subject to be eligible for the study, a run-in period of at least two weeks with the modified PD prescription should take place. The change in prescription will be made after assessment by the responsible physician to ensure that the new prescription is clinically comparable to the current prescription. Such a change will require the subject to consent to a change of PD prescription on the Patient Informed Consent Form. After the run-in period physician will review the eligibility of the patient to continue the study and complete the inclusion of the patient (enrolment point) **or** alternatively exclude the patient from the study. The exclusion of the patient will be recorded as a screening failure and the subject will not be further followed up in the study.

If patients treated with PD therapies have regular clinical checkups the Investigator may either approach the patient during these visits or by other means. After the patient has signed the ICF they are allocated a specific study number, which is used in the investigation documents and consecutive number are allocated with continued inclusion at each site.

Approximately 25 patients will be enrolled in this clinical investigation with a goal of 19 completing the study per protocol. Patients will be enrolled across six (6) to twelve (12) European sites.

There will be a competitive enrolment without a minimum enrolment for each site.

All patients recruited in the clinical investigation shall be accounted for, including those who withdraw from the investigation. The total duration of the patient's participation is around 12 weeks depending upon when it is suitable for the patients to schedule the study visits. The total time for recruitment and study completion is estimated to be approximately 12 months (including an estimated 9-month enrolment period).

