### 7.1.1 Sample size

The primary objective in the present study is to compare the UF volume obtained with the Carry Life® UF device, at the glucose dose determined by the UF volume obtained during the in-clinic phase of the study, and the UF volume obtained by a standard 2.27% glucose dwell of the same duration when performed by the patient at home. Carry Life® UF is intended as an intermittent treatment in order to provide an additional removal of fluid in patients whose UF need is not met by their standard PD regimen. A UF volume  $\geq$  250 ml greater with the Carry Life® UF treatment than with the 2.27% glucose CAPD dwell is considered a clinically relevant UF volume. Assuming three 5-hour treatments with Carry Life® UF per week this corresponds to an increase in fluid removal of 750 ml/week.

The sample size is calculated using the UF volume data from a previous pilot study (Tmed-007) on eight subjects, with the aim to demonstrate a superiority margin,  $\delta$ , of 250 ml. For each subject the  $\delta$  UF volume between the control 2.27% CAPD dwell and the Carry Life® UF treatment (paired comparison) at either the 11 g/h or the 14 g/h glucose dose provided input to the sample size calculation. The glucose dose providing input was selected following the dose determination scheme described for the current study (refer to page 47). The difference between the Carry Life® UF and the control 2.27% CAPD dwell had a mean value of 574 ml and a standard deviation of 236 ml.

The sample size is estimated by

$$n = \frac{(z_\alpha + z_\beta)^2 \sigma_m^2}{2(\epsilon - \delta)^2}$$

where

$\epsilon$  = test - control

$\delta$  = superiority margin

$\sigma_m$  = standard deviation of the paired differences

Set

$\text{Alpha} = 0.025, Z_{\text{alpha}} = 1.96$

$\text{Power} = 0.80, Z_{\beta} = 0.842$

$\sigma_m = 236$

$\epsilon = 574$

$\delta = 250$

Assuming a standard deviation of 236 ml, an expected difference of 574 ml and a superiority margin of 250 ml requires a sample size of 3 to obtain 80% power for the superiority test ( $\alpha = 0.025$ ) using a one sample superiority (one-sided) t-test sample size calculation.

We also consider a more extreme case where we assume a standard deviation of 1.4 times the previous standard deviation, or 330 ml. Further, we lower our assumed mean difference to 400 ml (about 0.7s below the previous observed value). With these assumptions (standard deviation of 330

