### 7.1.5 Randomization method

The randomization will occur after the in-clinic phase of the study, after the glucose dose the subject will use in the Carry Life® UF arm has been determined (refer to page 47 for a description of the dose determination). The randomization is being done to reduce any potential for bias based on subjects starting in the treatment or control arms. For each Carry Life® UF glucose dose (11 g/h and 15 g/h) the subjects will be randomized with an equal ratio (1:1) to start with either the control or the Carry Life® UF study arm. The randomization is based on block randomization using blocks of four, to ensure a balance between those who starts with control and those who starts with the Carry Life® UF arm. Subjects using the 11 g/h will be randomized to Group A or Group C. Subjects using the 15 g/h will be randomized to Group B or Group D. Group A and Group B will start with control. Group C and Group D will start with Carry Life UF. The randomization is a feature of the eCRF and will be managed centrally.

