### 7.1.6 Statistical analysis of primary endpoint

The primary endpoint uses the UF measured per protocol at each efficacy evaluation treatment during the home treatment phase. Each subject is expected to have two efficacy evaluations per treatment arm. Subjects with one or more per protocol efficacy evaluations in each arm will be included in the primary endpoint analysis. The analysis will be performed for both the ITT and the PP population. Excluded subjects will be tabulated with narratives as to why they are missed efficacy evaluations.

For each subject, we use the mean  $UF_{CL}$  and the mean  $UF_{CAPD}$  for analysis. The mean difference (i.e., a paired comparison) between the UF achieved with the Carry Life® UF treatment and the UF achieved with the control CAPD dwell ( $UF_{CL}(n) - UF_{CAPD}$ ) will be calculated ( $UF_{diff}(n)$ ) with a 95% CI. A superiority (one sided t-test) test will be used to demonstrate that the Carry Life UF treatment is superior to the control with superiority margin of 250 ml. A superiority margin greater than 0 ml but less than 250 ml supports that the Carry Life® UF treatment increases UF as compared to the control, but at a level that may not be clinically significant.

For the primary endpoint analysis, the four groups (Group A, 11 g/h starting with control; Group B, 15 g/h starting with control, Group C, 11 g/h starting with Carry Life UF; Group D, 15 g/h starting with Carry Life UF) in the randomization scheme will be pooled. Control data generated from all four groups will be part of the control group and Carry Life UF data for both doses from all four groups will be part of the Carry Life UF group. This results in two final groups for primary endpoint analysis; control and Carry Life UF. Based on 1) prior pilot study results showing no significant difference between the doses and 2) our dose determination procedure, which assigns the glucose dose to be used by each subject based on the UF result in the in-clinic phase of the study, we expect the two Carry Life UF glucose dose groups to behave as a single population and be poolable for the purposes of the primary endpoint of the study. However, as part of our descriptive analysis, we intend to summarize the difference in UF volume between study arms for each Carry Life UF glucose dose as well as for different fill volumes.

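### The printed rejection rule for the primary test points the wrong way, and its n cannot be reconciled with 19 as the total number of completers

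*Protocol*

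**What the plan says.** - **Section 5.2, primary endpoint hypothesis.** H0 is μ_d ≤ δ and H1 is μ_d > δ, where δ "is the superiority margin of 250 ml". The decision rule follows: "Where $H_0$ is rejected if the following is true", then (estimate − δ)/(σ_m/√(2n)) < t(α, 2n−2). The section does not define n.
- **Section 7.1.1, sample size.** The formula is n = (z_α + z_β)² σ_m² / [2(ε − δ)²], with the same factor 2. It defines σ_m as the "standard deviation of the paired differences" and describes the pilot-based figure as obtained "using a one sample superiority (one-sided) t-test sample size calculation". The conservative case gives 19.
- **Section 6.3.1 and the synopsis.** About 25 patients are to be enrolled "with a goal of 19 completing the study per protocol", so 19 is used as a total.
- **Section 7.1.5.** Within each dose, subjects are "randomized with an equal ratio (1:1) to start with either the control" or the device arm.
- **Section 7.1.6.** Each subject contributes one mean per arm, hence one paired difference, and a 95% CI for the mean difference is planned. On the test itself the section says: "A superiority (one sided t-test) test will be used to demonstrate that the Carry Life UF treatment is superior to the control". The margin named there is again 250 ml.

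**The concern.** There are two separate faults in the one formula that decides the trial.

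**Direction.** A test of H1: μ_d > 250 ml must reject for large values of the statistic. The printed rule rejects for small ones, so the worse the device performs, the more often H0 is rejected. The protocol therefore gives two conflicting rules for its primary test, and the one written as a formula is wrong.

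**Meaning of n.** Reversing the sign does not settle the matter. With one paired difference per subject and σ_m the SD of those differences, the standard error for N subjects is σ_m/√N. The form √(2n) with 2n−2 df is right only if 2n is the number of subjects, that is, n per sequence. The protocol instead uses 19, from a formula with the same factor 2, as the total. Either the type I error exceeds the stated 0.025, or the planned total is half of what the formula requires.

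**Working it through.** **Inputs.** Margin 250 ml (5.2). One-sided α = 0.025, z = 1.96; power 0.80, z = 0.842; pilot difference 574 ml and SD 236 ml; conservative difference 400 ml and SD 330 ml (all 7.1.1). Total completers 19, enrolment 25 (6.3.1).

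**1. The plan's own figures reproduce.** (1.96 + 0.842)² = 7.851.
- Conservative case: 7.851 × 330² / (2 × 150²) = 19.0.
- Pilot case: 7.851 × 236² / (2 × 324²) = 2.08, rounded up to 3.
- Conservative case without the factor 2: 38.0.

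The stated 19 thus depends on the factor 2, under which 2n = 38 is the number of paired differences.

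**2. Direction of the printed rule.** Take 19 subjects in total, SD 330 ml, and n = 19 inserted as printed. Then t(0.975, 36) = 2.028. The printed statistic is √2 times the ordinary paired t, so the cut-off on the paired t (18 df) is 2.028/√2 = 1.434.

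| Reading of t(α, ·) | True difference 0 ml | 250 ml (H0 boundary) | 400 ml |
|---|---|---|---|
| Upper quantile: P(reject H0) | about 100% | 91.6% | 29.0% |
| Lower quantile: P(reject H0) | 96.7% | 8.4% | 0.05% |

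Rejection becomes less likely as the true difference rises on both readings, so no quantile convention rescues the inequality.

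**3. Sign corrected, n = total subjects.** H0 is then rejected when the paired t exceeds 1.434.
- Type I error with 19 subjects: P(T18 > 1.434) = 8.4%, against 2.5% intended.
- With 25 subjects: cut-off 2.011/√2 = 1.422, and P(T24 > 1.422) = 8.4%.
- Observed mean needed at SD 330 ml: 250 + 2.028 × 330/√38 = 359 ml. The correct rule needs 250 + 2.101 × 330/√19 = 409 ml.

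**4. Sign corrected, n = subjects per sequence.** The standard error σ_m/√(2n) and 2n−2 df are valid and the type I error is 2.5%. But n = 19 then means 38 subjects, with 78% power at 400/330 ml (36 df; 80% by the normal approximation).

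**5. Power of a valid test at the planned size.** One-sided 0.025 t-test with N−1 df, noncentral t:

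| N in total | 400 ml, SD 330 ml |
|---|---|
| 19 | 46.6% |
| 25 | 58.8% |
| 38 | 77.9% |
| 40 | 80.0% |

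At the pilot values (574 ml, SD 236 ml), 19 subjects give over 99.9%.

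**The case against.** **The intent is clear elsewhere.** H1 and section 7.1.6 both give the right direction, and no analyst would declare superiority because the device did worse. A paired t-test as described in 7.1.6 would use s/√N and N−1 df, so the 8.4% arises only if someone applies the 5.2 formula with n = 19. This stands in part: 8.4% is conditional, and the rejection rates for the printed inequality describe a rule unlikely to be run. It does not make the printed rule correct.

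**The symbol may have been misread.** The text was extracted by machine, so the inequality should be checked against the PDF. The inequalities in H0 and H1 just above it were read correctly, and the n problem does not depend on this symbol.

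**The 2n form suits a 1:1 two-sequence crossover.** It does, with n per sequence. The fault then moves to 7.1.1 and the completer target, since 19 per sequence is 38 in total. If n is the total, both formulas are wrong, because 7.1.1 should then give about 38. Reading 2n as two evaluations per subject fails: 7.1.6 averages them first, and σ_m is already the SD of the paired differences.

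**The trial is not underpowered for the pilot effect.** True, as the working shows. But section 7.1.1 rests the study size on the conservative case and claims 80% power there.

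**Conclusion.** The concern holds; the rule is wrong as written and must be fixed. The inequality in 5.2 contradicts its own H1 and the test in 7.1.6, subject only to a check of that one symbol against the PDF. Independently of it, no single meaning of n makes 5.2, 7.1.1 and the target of 19 completers all correct. With n as the total, the sign-corrected rule has 8.4% one-sided type I error instead of 2.5%, and the sample size formula is also off by a factor of 2. With n per sequence, the rule is valid but 38 subjects are required. On either reading, 19 completers give about 47% power in the conservative case. These figures assume normally distributed paired differences, one per subject, and the protocol's own SD of 330 ml.

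**What to change.** In section 5.2, replace the rule by: reject H0 if (mean paired difference − 250)/(s_d/√N) > t(0.975, N−1), where N is the total number of subjects analysed and s_d the SD of their paired differences. This is equivalent to the lower limit of the two-sided 95% CI already planned in 7.1.6 exceeding 250 ml. If a sequence effect is fitted, use the model standard error with N−2 df.

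In section 7.1.1, define n. If it is per sequence, say so, write N = 2n, and correct the completer target. If it is the total, remove the factor 2 and recompute: 38 by the normal approximation, 40 by the t-test, in the conservative case. Otherwise keep 19 and state the assumptions under which it gives 80% power.

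The text change is one formula and one definition. The possible larger cost is a change to the stated sample size, or to the power claimed for it.

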**Secondary endpoint hypotheses**

**Peritoneal sodium removal:** The peritoneal sodium removal achieved with the Carry Life® UF system is larger than the peritoneal sodium removal achieved with CAPD using a 2.27% glucose PD solution during a 5-hour treatment.

Hypothesis:

H0:  $\mu_{CL} \leq \mu_{CAPD}$

H1:  $\mu_{CL} > \mu_{CAPD}$

Where  $\mu_{CL}$  is the average paired Carry Life® UF peritoneal sodium removal and  $\mu_{CAPD}$  is the average paired CAPD peritoneal sodium removal.

**Glucose UF efficiency:** The glucose UF efficiency (ml UF volume / g glucose absorbed) achieved with the Carry Life® UF system is higher than the glucose UF efficiency achieved with CAPD using a 2.27% glucose PD solution during a 5-hour treatment.

Hypothesis:

H0:  $\mu_{CL} \leq \mu_{CAPD}$

H1:  $\mu_{CL} > \mu_{CAPD}$

Where  $\mu_{CL}$  is the average paired Carry Life® UF glucose UF efficiency and  $\mu_{CAPD}$  is the average paired CAPD glucose UF efficiency.

Peak dialysate glucose concentration:

H0: PeakCL dialysate glucose concentration  $\geq$  2.27%

H1: PeakCL dialysate glucose concentration  $<$  2.27%

Where peakCL is the highest measured dialysate glucose concentration during the Carry Life® UF treatment (T1h to T5h).

AEs and SAEs:

There is no statistical test for the safety endpoint. The AEs will be tabulated and described in detail.

### 5.3 CLAIMS OF PERFORMANCE OF THE DEVICE

Claims and intended performance of the investigational device to be verified include:

- A larger UF volume can be obtained compared to a standard 2.27% glucose CAPD dwell.
- A larger sodium removal can be obtained compared to a standard 2.27% glucose CAPD dwell.
- The device maintains the intraperitoneal glucose concentration throughout the treatment.
- The glucose concentration is maintained below 2.27% i.e., below the glucose concentration of a medium strength glucose PD solution.
- The system prevents increases in intraperitoneal volume by hourly drainage of approximately 180 ml of dialysate.
- The glucose UF efficiency (ml UF / g glucose absorbed) is improved compared to a standard 2.27% glucose CAPD dwell.

## 5.4 RISKS AND ANTICIPATED ADVERSE DEVICE EFFECTS TO BE ASSESSED

Anticipated adverse device effects are contained in Section 4.3 and the specific adverse device effects for evaluation are as follows:

- Adverse device effects associated with excessive UF volumes:
  - Hypotension.
  - Weight reduction below target weight.
  - Other clinical symptoms of dehydration.
  - Reduced residual renal function.
  - Changes in blood chemistry (electrolytes, glucose, albumin, parathyroid hormone [PTH]).
- Adverse device effects associated with glucose absorption/inadequate diabetes medication:
  - Hyperglycemia.
  - Hypoglycemia.

## 6 DESIGN OF THE CLINICAL INVESTIGATION

---

### 6.1 GENERAL

The clinical investigation is a pre-market, prospective, multicenter, randomized, crossover study in adult subjects with ESKD treated with CAPD.

The study consists of the following five phases:

1. Inclusion phase.
2. In-clinic treatment phase for dose determination and safety evaluation.
3. Randomization phase.
4. Transition to home phase.
5. Home treatment phase for efficacy and safety evaluation.

Patients need to use the Baxter PD system and have a PD prescription of at least one 2.27% glucose day dwell of 1.5-2 L to be included in the study. There is an optional run-in phase during the inclusion phase in order for the patient to meet the PD prescription inclusion criteria. Throughout the study, the subject will use the fill volume they normally use, both for the standard PD prescription and for the Carry Life® UF treatments. However, for the PET a 2 L fill volume will be used.

The in-clinic phase consists of one 2.27% CAPD dwell (PET) and two Carry Life® UF treatments (one at 11 g/h glucose and one at 15 g/h glucose). The Carry Life® UF treatments will be used for a safety evaluation, and based on the UF volumes achieved, the Carry Life® UF glucose dose for the home treatment phase will be determined.

After completion of the in-clinic phase, subjects will be randomized to start the home treatment phase either with the control treatment arm or with the Carry Life® UF treatment arm. Subjects in the control arm will continue their standard CAPD treatment. In the Carry Life® UF arm, one 2.27% glucose CAPD dwells per day will at three days of the week be replaced by a Carry Life® UF treatment. During the remaining four days of the week, one 2.27% glucose CAPD dwell will be replaced with a 1.36% glucose CAPD dwell.

The Carry Life UF system will be used during Mondays, Wednesdays and Fridays, instead of a 2.27% glucose dwell. The time of the day when the Carry Life® UF system will be used does not need to be at the same time of the day as the 2.27% glucose dwell. The time of the day when the Carry Life UF system will be used, may differ on different days based on the subject's schedule.

At four (4) efficacy evaluation days during the home treatment phase (two per arm), there will be a careful recording of the solution volumes used (PD solution and glucose solution), volumes drained, and samples will be taken from the drain bags after treatment. The subject, together with the responsible physician, will determine during which days and during what time of the day the efficacy evaluation treatments (the 2.27% glucose dwell during the control arm and the Carry Life® UF treatment during the Carry Life® UF arm) will be performed. For each subject all efficacy evaluation treatments shall be performed on the same day of the week and on the same time of the day. A 2.27% glucose dwell will be the comparator dwell during the control arm. In order to perform the comparator dwell and the Carry Life UF treatment during at the same time of day, the physician may

need to modify the order and duration of the CAPD day dwells during the efficacy evaluation days in the control arm home phase of the study.

AEs, SAEs, and Carry Life® UF device malfunctions will be collected throughout the study. A nurse at each participating clinic who has undergone education and training necessary for thorough AE collection will be responsible for the recording of AEs (i.e., education in good clinical practice [GCP] will be required and training with respect to the eCRF for AE reporting). In case of an AE or device malfunction in the home treatment phase, the subject will be instructed to immediately contact the clinic. Furthermore, the clinic will contact the subject weekly and specifically ask about the occurrence of any AE or Carry Life® UF device malfunction.

The patient's participation will be approximately 12 weeks. The actual time mainly depends on how frequent the three in-clinic visits are scheduled, how many training sessions are required, and the scheduling of the training visits. The study schedule will include 8 to 13 visits dependent on the individual device training requirements. Only the in-clinic visits and the visits during the home treatment phase have been assigned a specific visit number:

1. Inclusion phase – Screening & consent – Visit 1.
2. In-clinic treatment phase for dose determination efficacy and safety evaluation – Visits 2–4 (approximately 2 weeks).
3. Randomization phase – No visit.
4. Transition to home treatment phase – Visit T1 to T7 (2–7 visits, approximately 1 week).
5. Home treatment phase for efficacy and safety evaluation – Visit 5 and 6 (8 weeks; 4 weeks in the control arm and 4 weeks in the treatment arm).

The subject will be followed up for one week for new or continuing AEs after the end-of-study visit. The follow-up will be in the form of a phone call or a physical meeting as determined by the investigator.

There will be at least one day in between treatment during the in-clinic phase of the study. Any changes in medications or PD prescriptions will be recorded during the study. If changes to diuretic prescription or PD prescription are made, the reason for the change will be documented. If a study participant discontinues the study the reason for this will be documented in detail.

A flow diagram of the study design is shown in Figure 1 and Figure 2. Table 1 outlines the schedule of activities at each study visit.

